## **2.0 Study Objectives and Design**

### **2.1 Study Objectives, Hypotheses and Estimands**

The primary study objective, related to Study Period 1, is to assess the efficacy and safety of upadacitinib, initiated at 15 mg once daily (QD) and dose adjusted based on clinical response, compared with dupilumab as per its label. An additional objective, related to Study Period 2, is to assess the efficacy and safety of upadacitinib, initiated at 15 mg QD and dose adjusted based on clinical response, in subjects with inadequate response to dupilumab and treated at 30 mg QD in subjects with inadequate response to upadacitinib in Period 1. The primary efficacy objective is based on the achievement of an at least 90% reduction in EASI from baseline (EASI 90) and a Worst Pruritus Numerical Rating Scale of 0 or 1 (WP-NRS 0/1) at Week 16 with the treatment of upadacitinib compared with dupilumab in the Intent-to-Treat (ITT) Population, which consists of all randomized

subjects. The secondary efficacy objectives are based on ranked secondary endpoints as defined in Section 3.2 (below) with the treatment of upadacitinib compared with dupilumab in the ITT Population.

The hypothesis corresponding to the primary efficacy endpoint (Section 3.1) is:

The proportion of subjects achieving EASI 90 and WP-NRS 0/1 at Week 16 in those treated with upadacitinib is greater than those treated with dupilumab.

The estimand corresponding to the primary endpoint is defined using the composite variable strategy, as follows:

Difference in the proportion of subjects achieving EASI 90 and WP-NRS 0/1 at Week 16 without the use of rescue medication between upadacitinib and dupilumab in the adolescents and adult subjects with moderate to severe AD who have inadequate response to systemic therapy.

The hypotheses and estimands corresponding to the ranked secondary endpoints are summarized below.

Hypotheses: the proportion of subjects achieving each ranked endpoint in those treated with upadacitinib is greater than those treated with dupilumab.

Estimands: Difference in proportion of subjects achieving each of ranked secondary endpoints without the use of rescue medication between upadacitinib and dupilumab in adolescents and adult subjects with moderate to severe AD who have inadequate response to systemic therapy.

The primary analysis will be conducted after all ongoing subjects have completed the Week 16 visit or permanently discontinued Period 1, and all data pertaining to Period 1 are cleaned. This analysis is the final and only analysis for the primary and ranked secondary endpoints.

## 2.2 Study Design Overview

This is a global, Phase 3b/4, randomized, open-label, efficacy assessor-blinded, multi-center study that will evaluate upadacitinib compared with dupilumab, as monotherapy, in adolescents and adult subjects ( $\geq 12$  and  $< 64$  years of age weighing at least 40 kg) with moderate to severe AD who have inadequate response to systemic therapy. Eligible subjects must have a documented history of inadequate response to at least one systemic treatment for AD prior to the Baseline Visit or for whom other systemic treatments are otherwise medically inadvisable.

The study will consist of a 35-day Screening Period; Period 1, a 16-week randomized, open-label, efficacy assessor blinded treatment period for all subjects, and a 30-day or 12-week follow-up visit for subjects on upadacitinib or dupilumab respectively, who will not enter the Period 2; Period 2, a 16-week open-label, efficacy assessor blinded extension period for those subjects with a  $< \text{EASI } 75$  response at Week 16 (total duration 32 weeks) and a 30-day follow-up visit. The 30-day or 12-week follow-up visit or phone call (for subjects on upadacitinib or dupilumab, respectively) following the last dose of study drug will not be required for any subject who initiates commercially available upadacitinib or dupilumab upon the Study Completion visit or Premature Discontinuation visit.

Sites will have the option to conduct the unscheduled visits/30-day or 12-week follow-up visit virtually during the course of the study as needed:

The study is comprised of two periods:

**Period 1:** A 16-week open-label, efficacy assessor blinded treatment period designed to evaluate the efficacy and safety of upadacitinib, initiated at 15 mg QD and dose adjusted based on clinical response starting after 4 weeks of treatment, compared with dupilumab as per its label. Subjects who meet eligibility criteria will be randomized in a 1:1 ratio to receive either upadacitinib 15 mg QD or dupilumab as per its label.

**Period 2:** An extension period to evaluate the efficacy and safety of upadacitinib, initiated at 15 mg QD and dose adjusted based on clinical response in subjects with inadequate

response to dupilumab and treated at 30 mg QD in subjects with inadequate response to upadacitinib in Period 1. At Week 16 subjects from both treatment arms with a < EASI 75 response will enter Period 2; subjects from the dupilumab arm will be offered the option to receive upadacitinib 15 mg QD while subjects from the upadacitinib arm will either continue (if already receiving 30 mg) or be escalated to upadacitinib 30 mg QD (if receiving 15 mg QD) until Week 32.

The details for Upadacitinib/Dupilumab arms and the dose adjustment for each treatment arm in each study period can be found in Protocol Section 4.1.

[figure not shown]
The primary analysis for the study will be performed when all ongoing subjects have completed Week 16 or permanently discontinued Period 1, and all data pertaining to Period 1 are cleaned. This analysis is the final and only analysis for the primary and ranked secondary endpoints. Additional analyses may be performed as appropriate.

The schematic of the study is shown in [Figure 1](#).

**Figure 1. Study Schematic**

**Figure 1. Study Schematic**

BL = Baseline; EOW = every other week; EASI 50/75 = Eczema Area and Severity Index 50/75; QD = once daily;  
SC= subcutaneous; vIGA-AD = Validated Investigator's Global Assessment for Atopic Dermatitis

## 2.3 Treatment Assignment and Blinding

All subjects will be assigned a unique identification number by the IRT at the Screening Visit. For subjects who rescreen, the screening number assigned by the IRT at the initial Screening Visit should be used. The IRT will assign a randomization number that will encode the subject's treatment group assignment according to the randomization schedule generated by the statistics department at AbbVie.

During Period 1, subjects who meet eligibility criteria will be randomized in a 1:1 ratio to one of the two arms as shown below:

**Upadacitinib arm (N = 440):**

Daily oral doses of upadacitinib 15 mg QD with potential dose escalation to upadacitinib 30 mg QD if any of the following parameters is met:

- Starting at Week 4, subject has a < EASI 50 response
- Starting at Week 4, subject has a < 4-point improvement from Baseline in WP-NRS (weekly average)
- Starting at Week 8, subject has a < EASI 75 response

At Week 16, subjects will be reassigned based on their EASI response:

- < EASI 75 will be allocated or continue to receive oral doses of upadacitinib 30 mg QD in Period 2
- $\geq$  EASI 75 will complete end of study procedures.

**Dupilumab arm (N = 440):**

Adults: Dupilumab 600 mg (2  $\times$  300 mg dupilumab SC injection) administered at the Baseline visit, followed by dupilumab 300 mg SC injection EOW until the Week 16 visit.

Adolescents: Dose of dupilumab for subcutaneous administration in adolescent patients (12 to 17 years of age and weighing at least 40 kg) with AD will be based on body weight of subject at Screening Visit and at each visit:

- 40 to < 60 kg: initial dose: 400 mg (two 200 mg injections) and subsequent doses (EOW): 200 mg
- 60 kg or more: initial dose: 600 mg (two 300 mg injections) and subsequent doses (EOW): 300 mg

At Week 16, subjects receiving dupilumab as per its label will be reassigned based on their EASI response:

- $<$  EASI 75 will be offered the option to receive oral doses of upadacitinib 15 mg and enter Period 2
- $\geq$  EASI 75 will complete end of study procedures

During Period 2, subjects randomized to upadacitinib 15 mg QD will have their dose increased to 30 mg QD if any of the following parameters is met:

- Starting at Week 20, subject has a  $<$  EASI 75 response
- Starting at Week 20, subject has a  $<$  4-point improvement from Baseline in WP-NRS (weekly average)

An unscheduled visit may be used for this purpose if necessary for dose escalation\*.

Randomization will be stratified by baseline vIGA-AD categories [3;4] and age categories (12 to  $<$  18; 18 to  $<$  40;  $\geq$  40 to  $<$  64 years).

The blinded efficacy assessor will remain blinded to each subject's treatment through Week 32. Subjects and other study site personnel will be aware of the subject's treatment assignment.

\* The subjects are considered as escalating dose to upadacitinib 30 mg QD in analysis if the subjects received the drug dispensation of upadacitinib 30 mg QD.

## **2.4 Sample Size Determination**

Approximately 880 subjects will be randomized to upadacitinib or dupilumab in a 1:1 ratio. Assuming a response rate of 12% in achieving both EASI 90 and WP-NRS 0/1 at Week 16 in the dupilumab arm, this sample size will provide more than 90% power to detect the treatment difference of 17% (upadacitinib versus dupilumab), using a two-sided significant level of 0.05. Sample size calculations were performed using nQuery Version 9.1.1.0.

### **3.0 Endpoints**

#### **3.1 Primary Endpoint**

The primary endpoint is the achievement of both EASI 90 and WP-NRS 0/1 at Week 16.

#### **3.2 Secondary Endpoints**

Ranked Secondary Endpoints are as follows.

1. Achievement of EASI 90 at Week 16.
2. Achievement of WP-NRS 0/1 at Week 16 among subjects with Baseline WP-NRS > 1.
3. Achievement of an improvement (reduction) in WP-NRS  $\geq 4$  at Week 16 among subjects with Baseline WP-NRS  $\geq 4$ .
4. Achievement of WP-NRS 0/1 at Week 4 among subjects with Baseline WP-NRS > 1.
5. Achievement of WP-NRS 0/1 at Week 2 among subjects with Baseline WP-NRS > 1.
6. Achievement of EASI 90 at Week 4.
7. Achievement of EASI 75 at Week 2.
8. Achievement of EASI 100 at Week 16.

#### **3.3 Additional Efficacy Endpoints**

In addition to the visits for the primary and ranked secondary efficacy endpoints in Section 3.1 and Section 3.2, the primary and ranked secondary efficacy endpoints will also be evaluated at the other scheduled visits in Period 1 and Period 2.

The following endpoints will also be evaluated at all scheduled visits in Period 1 and Period 2 (if applicable) during which the assessments are measured as noted in the Study Activities Table:

- Achievement of EASI 75/90/100 at Week 32 for subjects who received dupilumab/upadacitinib in Period 1 and did not achieve EASI 75 at Week 16.
- Achievement of EASI 90 AND WP-NRS 0/1 at Week 32 for subjects who received dupilumab/upadacitinib in Period 1 and did not achieve EASI 90 AND WP-NRS 0/1 at Week 16.
- Achievement of an improvement (reduction) in WP-NRS  $\geq 4$  at Week 32 for subjects who had WP-NRS  $\geq 4$  at Baseline and who received dupilumab/upadacitinib in Period 1 and did not achieve WP-NRS reduction  $\geq 4$  at Week 16.
- Achievement of WP-NRS 0/1 at Week 32 for subjects who had WP-NRS  $> 1$  at Baseline and who received dupilumab/upadacitinib in Period 1 and did not achieve WP-NRS 0/1 at Week 16.
- Achievement of 75% reduction in EASI in each body region from Baseline.
- Achievement of 75% reduction in EASI in the head and neck body region at Week 32 for subjects who received dupilumab/upadacitinib in Period 1 and did not achieve 75% reduction in EASI in the head and neck body region at Week 16.

### **3.4 Safety Endpoints**

The following endpoints will be included in the safety analyses:

- Treatment emergent adverse events (TEAEs);
- Serious adverse events (SAEs);
- Adverse events of special interest (AESIs);
- Other Safety Topics of Interest;
- Adverse events (AEs) leading to discontinuation;
- Vital signs and laboratory tests.

Laboratory assessments will include hematologic parameters, chemistry, liver function tests, and lipid parameters.

## **4.0 Analysis Populations**

Significant non-compliance was identified at a site. As a result of this finding, subjects enrolled in this site will not be included in any analysis population and data collected from this site will not be included in any analysis.

The following population sets will be used for the analyses.

- The Intent-to-Treat (ITT) Population of Period 1 (ITT 1 Population) consists of all subjects who were randomized at Baseline.
- The ITT Population of Period 2 (ITT 2 Population) consists of all subjects who were randomized at Baseline and continue in Period 2.

The ITT Populations will be used for all efficacy analyses. Subjects will be included in the treatment group to which they are randomized.

The below Safety Populations will be used to provide a comprehensive summary of safety based on treatment received in Period 1 and Period 2 respectively.

- The Safety Population of Period 1 (Safety 1 Population) consists of all randomized subjects who received at least 1 dose of study drug in Period 1.
- The Safety Population of Period 2 (Safety 2 Population) consists of all randomized subjects who received at least 1 dose of study drug in Period 2.
- All Upadacitinib treated Population (ALL UPA Population) consist of all subjects who received at least one dose of upadacitinib in the study.

For safety analyses, subjects will be analyzed based on the treatment received.

The analyses populations for efficacy and safety analyses are summarized in the following table.

**Table 1. Analyses Populations: ITT Populations and Safety Populations**

Analyses Populations	Study Period	Analyses Groups
ITT 1	Period 1	Dupilumab
		Upadacitinib a
ITT 2	Period 2	Upadacitinib/Upadacitinib 30 mg
		Dupilumab/Upadacitinib b
Safety 1	Period 1	Dupilumab
		Upadacitinib 15 mg c
		Upadacitinib a
Safety 2	Period 2	Upadacitinib/Upadacitinib 30 mg
		Dupilumab/Upadacitinib b
ALL UPA	During the upadacitinib administration	Upadacitinib 15 mg
		Upadacitinib 30 mg
		Any UPA d

- a. Upadacitinib subjects regardless of the dose level in Period 1.
- b. Dupilumab/Upadacitinib subjects regardless of the upadacitinib dose level in Period 2.
- c. Upadacitinib 15 mg subjects (who never received UPA 30 mg QD) in Period 1.
- d. Subjects who received at least one dose of upadacitinib regardless of the dose level in the study.

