- **Upadacitinib arm (N = 440):** Daily oral doses of upadacitinib 15 mg QD from the Baseline visit until the Week 16 visit. During Period 1, subjects randomized to upadacitinib 15 mg QD will have their dose increased to 30 mg QD if any of the following parameters is met:
 - Starting at Week 4, subject has a < EASI 50 response
 - Starting at Week 4, subject has a < 4-point improvement from Baseline in WP-NRS (weekly average)
 - Starting at Week 8, subject has a < EASI 75 responseAt Week 16, subjects receiving upadacitinib 15 mg QD or 30 mg QD, will be reassigned based on their EASI response:
 - < EASI 75 will be allocated or continue to receive oral doses of upadacitinib 30 mg QD in Period 2
 - ≥ EASI 75 will complete end of study procedures.
- **Dupilumab arm (N = 440):**
 - Adults: Dupilumab 600 mg (2 × 300 mg dupilumab SC injection) administered at the Baseline visit, followed by dupilumab 300 mg SC injection EOW until the Week 16 visit.
 - Adolescents: Adolescents (12 to 17 years of age and weighing at least 40 kg).

Dose of dupilumab for subcutaneous administration in adolescent patients 12 to 17 years of age with AD.

Body weight of subject at Screening Visit and at each visit:

1. 40 to < 60 kg:
 - Initial dose: 400 mg (two 200 mg injections)
 - Subsequent doses (EOW): 200 mg
2. 60 kg or more:
 - Initial dose: 600 mg (two 300 mg injections)
 - Subsequent doses (EOW): 300 mg
- At Week 16, subjects receiving dupilumab as per its label will be reassigned based on their EASI response:
 - < EASI 75 will be offered the option to receive oral doses of upadacitinib 15 mg QD and enter Period 2
 - \geq EASI 75 will complete end of study procedures
- During Period 2, subjects randomized to upadacitinib 15 mg QD will have their dose increased to 30 mg QD if any of the following parameters is met:
 - Starting at Week 20, subject has a < EASI 75 response
 - Starting at Week 20, subject has a < 4-point improvement from Baseline in WP-NRS (weekly average)

An unscheduled visit may be used for this purpose if necessary for dose escalation.

Any subject treated for at least 8 weeks with upadacitinib 30 mg QD with a < EASI 50 response (reduction from Baseline) after rescue with topical corticosteroid treatment for at least 1 week must be discontinued.

[figure not shown]

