### **Study Drug Duration (in Days) in Period 1:**

Duration of upadacitinib in Period 1 is defined for each subject as

- For subjects who do not continue into Period 2:  
Date of the last dose of study drug in the Period 1 - Date of the first dose of study drug in Period 1 + 1

- For subjects who continue into Period 2:  
Minimum of (Date of the first dose of study drug in Period 2 - Date of first dose of study drug in Period 1, Date of the last dose of study drug in Period 1 - Date of first dose of study drug in Period 1 + 1)

Duration of upadacitinib 15mg for subjects who have never experienced dose escalation in Period 1 is defined as

- Date of the last dose of upadacitinib 15 mg in the Period 1 - Date of the first dose of upadacitinib 15 mg in Period 1 + 1

Duration of dupilumab in Period 1 is defined for each subject as

- For subjects who do not continue into Period 2:  
Last dose date of dupilumab in Period 1 - first dose date of dupilumab in Period 1 +14
- For subjects who continue into Period 2:  
Minimum of (Date of the first dose of upadacitinib in Period 2 - Date of first dose of dupilumab in Period 1, Date of last dose dupilumab in Period 1 - Date of first dose of dupilumab in Period 1 + 14)

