### **10.2 Adverse Events**

The summaries of adverse events will be provided by treatment groups (defined in [Table 1](#)) in Period 1 for Safety 1 Population, in Period 2 for Safety 2 Population, and during the administration of upadacitinib for All UPA Population.

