### 10.2.1 Treatment-Emergent Adverse Events

Treatment-emergent adverse events (TEAEs) are defined as follows:

- TEAEs in Period 1 are defined as any adverse events that begin or worsen in severity after initiation of upadacitinib/dupilumab through the minimum (30 days following the last dose of upadacitinib in Period 1 or through 84 days following the last dose of dupilumab in Period 1, the start day of Period 2 – 1).
- TEAEs in Period 2 are defined as any adverse events that begin or worsen in severity after initiation of upadacitinib in Period 2 through 30 days following the last dose of upadacitinib in Period 2.
- TEAEs during the administration of upadacitinib are defined as any adverse events that begin or worsen in severity after initiation of upadacitinib through 30 days following the last dose of upadacitinib.

If a missing or an incomplete onset date is collected for an adverse event, the event will be assumed to be treatment-emergent unless there is other evidence that confirms that the event is not treatment-emergent (e.g., the event end date is prior to the study drug start date). Events where the onset date is the same as the study treatment start date are assumed to be treatment-emergent. All treatment-emergent AEs will be summarized overall, as well as by primary MedDRA SOC and Preferred Term. The SOCs will be presented in alphabetical order, and the PTs will be presented in alphabetical order within each SOC.

The number and percentage of subjects experiencing TEAEs and the number of events per 100 patient-years of exposure will be summarized.

TEAEs per 100 patient-years of exposure are defined as the number of TEAEs divided by the total exposure in 100 patient-years. See the calculation method below:

$$100 * (\text{Number of TEAEs}) / (\text{Total Patient Years})$$

where total patient years is defined as the sum of the study drug duration (defined in Section 6.0) of all subjects normalized by 365.25 and rounded to 1 decimal place.

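### The Period 1 'Upadacitinib 15 mg' safety column is selected on later response, so it cannot be read as the safety of 15 mg beside dupilumab

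*SAP*

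**What the plan says.** SAP Section 4.0, Table 1, lists three Safety 1 groups for Period 1: dupilumab; a 15 mg group, footnoted "Upadacitinib 15 mg subjects (who never received UPA 30 mg QD) in Period 1"; and a pooled group, footnoted "Upadacitinib subjects regardless of the dose level in Period 1". There is no 30 mg group in Safety 1.

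SAP Section 6.0 gives the 15 mg group its own exposure: "Duration of upadacitinib 15mg for subjects who have never experienced dose escalation in Period 1 is defined as" the span from first to last 15 mg dose. The 15 mg weeks of a subject who later escalates are not counted in that duration.

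SAP Section 10.2 applies these groups to adverse events: "The summaries of adverse events will be provided by treatment groups". Section 10.2.1 reports percentages and events per 100 patient-years, "where total patient years is defined as the sum of the study drug duration (defined in Section 6.0) of all subjects".

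Protocol Section 4.1 starts the whole upadacitinib arm on 15 mg. The first two escalation triggers open at Week 4: "Starting at Week 4, subject has a < EASI 50 response", and less than a 4-point itch improvement. A third (below EASI 75) opens at Week 8. Under Protocol Section 5.6, a subject who stops study drug leaves the study.

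**The concern.** Whether a subject belongs to the 15 mg group is not known at the first dose. It is settled by what happens from Week 4 onward. A subject who stops for an adverse event before Week 4 never has the chance to escalate and always stays in. A subject who escalates is removed, together with at least about four weeks of 15 mg treatment and any events in that time.

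This is the only 15 mg display set beside dupilumab in Period 1. Protocol Section 4.2 says the trial should help inform the use of both approved doses, so readers will be drawn to a column headed with the 15 mg dose. SAP Section 4.0 also says that safety is analysed by treatment received. Escalators did receive 15 mg, yet their time on it is left out of the 15 mg group.

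**Working it through.** **Inputs from the documents.** 440 subjects in the upadacitinib arm; a 16-week Period 1; first possible escalation at Week 4. The plan gives no escalation share, stopping rate or adverse-event rate, so there is no figure of its own to reproduce on this point.

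**Assumptions.** A share *e* of those still on drug at Week 4 escalates then; the range is 20-60%. The 16-week risk of an adverse event that ends treatment is 4%, with constant hazard unrelated to response.

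**1. Events that end treatment.** An escalator cannot have had such an event while on 15 mg. Dropping escalators therefore removes person-time and no events. Ignoring the small loss to stopping, 15 mg weeks per subject are 4 + 12(1 − e) = 16 − 12e in full and 16(1 − e) in the column, so

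ratio of column rate to rate on all 15 mg time ≈ (16 − 12e)/(16 − 16e).

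At e = 0.2 this is 13.6/12.8 = 1.06; at e = 0.5, 10/8 = 1.25; at e = 0.6, 8.8/6.4 = 1.375.

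Allowing for stopping, with hazard λ = −ln(0.96)/16 per week:

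| e | Subjects in column | Events | Per 100 PY, all 15 mg time | Per 100 PY, column | Ratio | Column % |
|---|---|---|---|---|---|---|
| 20% | 353 | 15.0 | 13.3 | 14.2 | 1.06 | 4.24 |
| 30% | 309 | 13.7 | 13.3 | 14.8 | 1.11 | 4.42 |
| 40% | 266 | 12.3 | 13.3 | 15.6 | 1.17 | 4.65 |
| 50% | 222 | 11.0 | 13.3 | 16.7 | 1.25 | 4.96 |
| 60% | 179 | 9.7 | 13.3 | 18.3 | 1.38 | 5.44 |

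The percentage is [(1 − S4) + (1 − e)(S4 − S16)]/(1 − e·S4), with S4 = 0.9898 and S16 = 0.96. At e = 0.3 this is (0.0102 + 0.7 × 0.0298)/(1 − 0.3 × 0.9898) = 0.0310/0.7030 = 4.4%. A simulation at e = 0.3 gave 13.4 on all 15 mg time against 14.8 in the column. Letting 30% escalate at Week 4 and 20% of the remainder at Week 8 gives a ratio of 1.26. Ratios at 2% and 6% risk are practically the same.

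**2. Dependence on timing.** If all stopping with probability *d* fell before Week 4, the column would show d/[d + (1 − d)(1 − e)]. For d = 0.04 and e = 0.3, 0.5, 0.7 this is 0.04/0.712 = 5.6%, 0.04/0.52 = 7.7% and 0.04/0.328 = 12.2%. The same 4% spread evenly over 16 weeks shows as 4.4%, 5.0% and 6.2%.

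**3. Events that do not end treatment, per patient-year.**
- Constant hazard unrelated to response: ratio 1.00.
- Hazard doubled in the first four weeks: the column has 20/16 units per week and all 15 mg time has (8 + 12(1 − e))/(4 + 12(1 − e)). At e = 0.2, 1.25/1.294 = 0.97; at e = 0.6, 1.25/1.455 = 0.86.
- Escalators with twice the rate of non-escalators on 15 mg: ratio (4e + 16(1 − e))/(8e + 16(1 − e)). At e = 0.3, 12.4/13.6 = 0.91; at e = 0.5, 10/12 = 0.83.
- Escalators with a lower rate (0.67 times): the ratio turns upward, 1.03 at e = 0.3 and 1.07 at e = 0.5.

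**4. Information dropped.** The share of 15 mg person-time left out is 4e/(4 + 12(1 − e)): 0.8/13.6 = 6% at e = 0.2 and 2.4/8.8 = 27% at e = 0.6.

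**5. Whether another planned output repairs it.** Subtracting the 15 mg column from the pooled column leaves escalators' 15 mg and 30 mg events mixed. The ALL UPA population has 15 mg and 30 mg groups without the never-escalated restriction. But it has no dupilumab column, Table 1 gives no rule for assigning events or time to a dose, and Section 6.0 gives it one overall duration from first to last upadacitinib dose. Neither output supplies the missing rate.

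**The case against.** The restriction is disclosed in Table 1 and Section 6.0. The SAP nowhere calls the column an unbiased 15 mg estimate, and no between-arm safety test is planned. The pooled column, which answers the primary objective of 15 mg adjusted on response, is untouched. All of this stands, and it limits the point to one descriptive column. Disclosure in a footnote does not change what the column heading invites.

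A reader might infer more than the documents support:
- *That escalators' 15 mg events vanish from reporting.* They do not; they are in the pooled Safety 1 column. They are missing only from the 15 mg column.
- *That every rate in the column is inflated.* Direction depends on the event type, and for some events there is no distortion per patient-year.
- *That a 4% stopping risk would show as 5.6-12.2%.* That needs all stopping before Week 4. The SAP tabulates discontinuation events over the whole of Period 1, and the documents say nothing about timing.
- *That the share of Week 0-4 events removed equals the escalation share.* Early stoppers keep their events in the column, so the two need not match.
- *That anyone who ever moves to 30 mg is excluded.* Footnote c covers Period 1 only; a subject first moved to 30 mg at Week 16 for Period 2 remains.

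Counting 15 mg time only up to escalation is also imperfect: the censoring is itself driven by response, and the rate leans on early weeks while dupilumab subjects contribute up to 16. That is a smaller and more visible limitation than discarding escalators altogether.

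**Conclusion.** The point holds for the Period 1 15 mg safety column. Its membership is fixed by a post-baseline outcome, this affects both percentages and exposure-adjusted rates, and no other planned output gives an unselected 15 mg rate beside dupilumab.

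The bias is moderate under the assumed inputs for events that end treatment, and larger if stopping clusters before Week 4. It reverses for early events or those commoner in escalators. Because the sign changes by event type, a reader cannot correct for it by eye. That the selection exists follows from the text alone; its size rests wholly on assumed escalation shares, risks and hazard shapes. The pooled safety comparison and all efficacy results are unaffected. The change should be made, but the trial's main conclusions do not depend on it.

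**What to change.** In SAP Table 1 (footnote c) and Section 6.0:

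1. Define the Period 1 15 mg display as all upadacitinib-arm subjects who took 15 mg. Count events and exposure from first 15 mg dose to the day before first 30 mg dose. For those who never escalate in Period 1, count events to the end of the Period 1 treatment-emergent window and keep the Section 6.0 last-dose convention for exposure. Report per 100 patient-years on 15 mg.
2. Apply the same dose-at-onset split to the ALL UPA 15 mg and 30 mg groups, with a duration for each dose.
3. If the never-escalated column is kept, head it 'never escalated in Period 1 (selected on response)'.
4. Footnote the limits: rates weighted to early weeks, response-driven censoring, and events soon after escalation counted under 30 mg.

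The cost is SAP wording and slightly more programming. The SAP already flags escalation from 30 mg dispensation (Section 2.3) and splits planned tablets before and after escalation for compliance (Section 6.0). It must say how the first 30 mg dose date is obtained, because dispensation and first dose can differ. No dosing or clinical rule changes.
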